## 1. Background

Obesity currently affects more than 1 in 3 adults in the US. An alarming consequence is the astounding increase in type 2 diabetes (T2D), which has emerged as the 7th leading cause of death. Lifestyle interventions have proved to be only modestly effective and rarely sustainable. Bariatric surgery, particularly Roux-en-Y gastric bypass (RYGB) is currently the most effective treatment for robust and sustained weight loss, and results in remarkable improvements in T2D status. However, these surgeries involve extensive and permanent re-arrangement of the GI tract, can be associated with serious complications, and are expensive. Conceivably they reach less than 2% of all eligible subjects. The ability to target the gut to treat obesity and diabetes without surgical intervention would represent a major therapeutic breakthrough. But, in order to accomplish this we must identify novel physiological targets and therapies.

### **Gut as a therapeutic target for obesity and diabetes: evidence from bariatric surgery**

The importance of the gut in nutrient metabolism and energy homeostasis is highlighted by the remarkable success of bariatric surgery. RYGB reduces stomach volume and diverts nutrient flow from the proximal intestine, which is a major site for nutrient sensing, absorption and transport to more distal segments of the small intestine. Digested nutrients absorbed by the enterocytes make their way directly to the bloodstream, or as in the case of lipids are delivered into the lacteals before entering the circulation. Nutrient sensing is mediated by enteroendocrine (EE) hormones that act locally to influence motility and digestive function, and relay nutritional status to the brain via vagal afferent nerve fibers, found in close proximity. The cell bodies of vagal afferent nerve fibers are located in the paired nodose ganglia and enter the brain stem via the tractus solitarius. They synapse onto neurons of the nucleus tractus solitarius (NTS) and dorsal motor nucleus of the vagus (DMV) where integration of sensory signals elicits cues for meal initiation, termination, and nutrient metabolism. Signaling across this gut-to-brain neuroendocrine axis is critical for regulation of feeding behavior, food intake, and energy homeostasis. We seek to exploit this neuroendocrine axis to impede nutrient uptake and manipulate the body's own sensory mechanisms in order to achieve a therapeutic end point for obesity and T2D without altering GI anatomy.

### **Manipulating sensory feedback from gut to influence nutrient metabolism**

Sensory feedback to the brain is based on the chemical milieu of the lumen and the distension status of the gut wall. Distension and contraction of the wall relay sensory signals of nutrient entry. This rhythmic contraction of the gut wall is the consequence of neurotransmission at presynaptic motor terminals, largely mediated by release of acetylcholine (Ach). Blocking this neurotransmission would prevent contraction of the smooth muscle wall and potentially relay a false sensory signal of nutrient entry and/or satiety.

Botulinum neurotoxins (BoNT), are some of the most potent anti-cholinergic agents that reduce muscle contraction. The most potent serotype A (available commercially as BOTOX®) has now been approved by the FDA for treatment of several neuromuscular conditions including blepharospasm, spasm, dystonia, spasticity, and even cerebral palsy in children. Botox possesses several unique pharmacological properties – it is specific, very potent, has limited diffusion from the injection site and is reversible. Based on its properties and evidence-based results, we propose to explore actions of Botox on the intestinal smooth muscle wall and its possible use in manipulating sensory feedback. If proved to be successful, this approach could provide a new treatment paradigm for T2D and metabolic diseases with or without obesity. This potential application of the drug has never been explored.

## 2. Rationale and Specific Aims

Botox has been approved by the FDA and successfully used for treatment of a variety of clinical syndromes related to abnormal muscle contraction. Its potential ability to impede intestinal wall contractions has never been explored. We seek to explore this novel application of the drug and its consequent effects on sensory feedback to the brain, feeding behavior, glucose tolerance, and weight gain. Based on its unique pharmacological properties, and our preliminary data in high-fat diet induced obese (DIO) mice, we hypothesize that Botox injected into the duodenal wall will (1) induce weight loss (2) improve glucose tolerance, and (3) improve duodenal nutrient sensing in obese, T2D subjects.

**Specific Aim 1.** Determine if Botox injected into the duodenum reduces body weight in obese, type 2 diabetic subjects

**Specific Aim 2.** Determine if Botox injected into the duodenum improves glucose tolerance in obese, type 2 diabetic subjects

[figure not shown]
**Specific Aim 3.** Determine if Botox injected into the duodenum improves nutrient sensing in obese, type 2 diabetic subjects

The information generated from the studies proposed may substantially alter our approach to tackle obesity and T2D, and lead to emphasis on the gut-brain cross talk in energy homeostasis.

## 3. Animal Studies and Previous Human Studies

### 3.1 Animal Studies

[figure not shown]
We have developed a surgical model for Botox injections in mice. Mice are anesthetized by isoflurane inhalation and laparotomy is performed to expose the intestines. Botox loaded into Hamilton syringes fitted with 30 g needles is injected into the smooth muscle layer of the duodenum at 3 sites, within 3 cm distal to the pyloric sphincter (Fig 1A) ensuring no drug diffusion into the lumen. High-fat (60%) diet induced obese (DIO) mice injected with

**Fig. 1A:** Duodenal injection site. **B:** Weight loss in DIO mice injected with saline or Botox (0.1-3U/kg body weight;  $n=3$ -4 mice)

Botox showed a dose-dependent decrease in body weight between 0.3-3U/kg body weight, and 3U/kg was observed to be the optimal dosage (Fig. 1B). The effects lasted for at least 7 weeks, following which they begin to dwindle and are almost reversed by the end of 10 weeks. Readouts analyzed to determine dosage and effective treatment time include body weight recordings, and protein expression of neurotransmitter, SNAP-25 and smooth muscle contraction marker phospho-myosin light chain 2Ser19 (P-MLCSer19). We also observed distension of the muscle wall and apparent dysmotility within 48 hours of injection that persisted until 6 weeks later. SNAP-25

Hamilton syringes fitted with 30 g needles is injected into the smooth muscle layer of the duodenum at 3 sites, within 3 cm distal to the pyloric sphincter (Fig 1A) ensuring no drug diffusion into the lumen. High-fat (60%) diet induced obese (DIO) mice injected with

**Fig. 2:** Representative WB of SNAP-25 expression in mice (A) kidney, stomach, colon, brain (for comparison) and duodenum injected with saline or Botox, measured 6 weeks later; P-MLCSer19 and total MLC expression (B) in duodenal injection site 1-10 weeks later.

expression at the Botox injection site was lower, suggesting that *Botox induced proteolysis of SNAP-25 (Fig 2A)*. P-MLCSer19, indicator of smooth muscle contraction in the gut was down-regulated also until 6 weeks, following which expression was restored (Fig 2B). These data suggest that Botox blocks smooth muscle contraction in the intestine.

1. *Botox causes weight loss in DIO mice (for up to 7 weeks post injections) without altering food intake:* DIO mice injected with Botox (3U/kg body weight) in the duodenal wall lost 15-20% body weight over 7 weeks compared to saline injected controls (Fig. 3). Interestingly, food intake was not significantly lower (data not shown), and thereby did not account for the robust weight loss observed.

2. *Botox improves glucose tolerance in DIO mice:* We observed significant improvement in glucose tolerance in Botox-treated DIO mice, measured 4 weeks after injection in the duodenal wall (3U/kg). Baseline OGTT was measured in a cohort of DIO mice ( $n=14$ ) prior to Botox injections. Three days later, saline ( $n=6$ ) or Botox ( $n=8$ ) was injected in the duodenal wall, and OGTT was repeated 4 weeks later. DIO mice started out with poor glucose tolerance, as expected. No improvement was observed in saline controls after 4 weeks; however, Botox-injected group showed strong improvement in glucose tolerance (Fig. 4).

### 3.2 Previous Human Studies

Botox for injections has been approved for treatment of overactive bladder (idiopathic or neurogenic detrusor over activity), upper and lower limb focal spasticity, cerebral palsy, primary axillary hyperhidrosis, strabismus, blepharospasm, cervical dystonia, and chronic migraine ( $\geq 15$  days per month with headaches lasting 4 hours or more a day).

Adverse reactions experienced in each of these approved conditions have been listed as under. In general, adverse reactions occur within the first week of injection.

[figure not shown]

Fig 4. OGTT in DIO mice before and after Botox injection (3U/kg). (A) Blood glucose before (baseline,  $n=14$ ) and 28 days after saline ( $n=6$ ) or Botox injection ( $n=8$ ). (C) Glucose AUC before and after Botox injection. \*,  $p<0.05$ ; \*\*,  $p<0.01$ .

#### Overactive bladder (OAB):

The table below lists the most common adverse reactions occurring within 12 weeks of BOTOX injections in placebo-controlled clinical trials for overactive bladder.

Table 1: Adverse reactions reported by patients treated for OAB in clinical trials

Adverse Reactions	BOTOX 100 Units (N=552)	Placebo (N=542)
Urinary tract infection	99 (18%)	30 (6%)
Dysuria	50 (9%)	36 (7%)

Urinary retention	31 (6%)	2 (0%)
Bacteriuria	24 (4%)	11 (2%)
Residual urine volume	17 (3%)	1 (0%)

During the entire study period, frequency of some of the above adverse reactions increased: urinary tract infections (26%), dysuria (11%), and bacteriuria (8%).

*Detrusor Overactivity associated with Neurologic Condition:*

The table below presents the adverse reactions reported in patients with detrusor over activity associated with neurologic condition within 12 weeks after intradetrusor Botox injections (200 Units).

Table 2: Adverse reactions reported by patients treated for detrusor over activity

Adverse Reactions	BOTOX 200 Units (N=262)	Placebo (N=272)
Urinary tract infection	64 (24%)	47 (17%)
Urinary retention	45 (17%)	8 (3%)
Hematuria	10 (4%)	8 (3%)
Fatigue	10 (4%)	3 (1%)
Insomnia	4 (2%)	0 (0%)

Some additional rare adverse events were reported including constipation (4%), muscular weakness (4%), dysuria (4%), fall (3%), gait disturbance (3%), and muscle spasms (2%).

*Chronic Migraine:*

The following adverse reactions were reported based on safety data compiled from two chronic migraine double-blind, placebo controlled phase 3 clinical trials involving 687 patients.

Table 3: Adverse reactions reported by patients treated for chronic migraine

Adverse Reactions by System Organ Class	BOTOX 155-195 Units (N=687)	Placebo (N=692)
Eye Disorders Eyelid Ptosis	25 (3.6%)	2 (0.3%)
Musculoskeletal & Connective Tissue Disorders Neck pain Musculoskeletal stiffness Muscular weakness Musculoskeletal pain Myalgia Muscle spasms	60 (8.7%) 25 (3.6%) 24 (3.5%) 18 (2.6%) 21 (3.1%) 13 (1.89%)	19 (2.7%) 6 (0.9%) 2 (0.3%) 10 (1.4%) 6 (0.9%) 6 (0.9%)
Nervous System Disorders Headache Migraine Facial paresis	32 (4.7%) 26 (3.8%) 15 (2.2%)	22 (3.2%) 18 (2.6%) 0 (0%)
Vascular Disorders Hypertension	11 (1.6%)	7 (1.01%)
Infections Sinusitis Bronchitis	28 (4.1%) 17 (2.5%)	27 (3.9%) 11 (1.6%)

Others		
Pain at injection site	23 (3.3%)	14 (2.0%)

**Primary Axillary Hyperhidrosis:**

Based on a cohort of 346 patients that received 50 Units and 110 patients that received 75 units of BOTOX in each axilla, about 3-10% of adults reported non-axillary sweating, pharyngitis, flu syndrome, pruritus, neck or back pain following injections.

**Blepharospasm:**

Patients with blepharospasm receiving an average of 33 units OF BOTOX per eye (3-5 injection sites) reported ptosis (21%), keratitis (6%), and eye dryness (6%) temporary facial paralysis and syncope were also reported.

**Strabismus:**

Strabismus patients receiving higher doses of BOTOX reported vertical deviation. About 17% of 2058 adults that received a total of 3650 injections for treatment of horizontal strabismus reported vertical deviation. Ptosis was reported in 1%, 16%, and 38% after injections in inferior rectus, horizontal rectus, and superior rectus, respectively. Retro bulbar hemorrhage was reported in 0.3% cases.

In general, local muscle weakness appears to be the most commonly reported and expected event following BOTOX injection in muscles. However, weakness of adjacent muscle tissues, and rarely remote tissues occurring as a result of “spread of toxin effect” have been reported in adult and pediatric patients as well. Events typically observed after any injection procedure including localized pain, inflammation, tenderness, bruising, erythema, and needle-related pain or anxiety have been reported in some clinical trials.

We will recruit obese subjects with pre-diabetes or T2D for the proposed clinical study for 5 visits. After informed written consent is obtained, subjects will be admitted to the Clinical Research Center (CRC), and will undergo upper endoscopic injection of Botox into the duodenal wall. We anticipate that injections of Botox into the duodenal wall will result in significant weight loss and improvements in glucose tolerance and duodenal nutrient sensitivity. Subjects will be studied over a period of 6 months. Subjects will be asked to complete 5 study visits: On the first visit, each subject will undergo an oral glucose tolerance test (OGTT). At visit 2, subjects will undergo an esophagogastroduodenoscopy (EGD) procedure for the delivery of BtX-A to the duodenal wall. Visits 3-5 will be made 1, 3, and 6 months after EGD (Figure 1). On every study visit, body weight and body composition will be recorded and oral glucose tolerance test (OGTT) be performed. Nutrient sensing test will be performed at visits 1 and 3.

#### **4. Inclusion/Exclusion Criteria**

***Inclusion Criteria***

1. Age = 18-65
2. BMI  $\geq 30 \text{ kg/m}^2$
3. Having established diagnosis of Type 2 diabetes or pre-diabetes

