## 5. Screening and Enrollment

Obese subjects ( $\text{BMI} \geq 30 \text{ kg/m}^2$ ) with prediabetes or type 2 diabetes ( $n = 20$ ) will be recruited by solicitation flyers, recruitment emails using Research Match and LISTSERV that reaches all Vanderbilt employees, residents, and students, and Facebook advertisements. Subjects who do not qualify for bariatric surgery, or subjects who are awaiting insurance approval for a bariatric procedure at the Center of Surgical Weight Loss, One Hundred Oaks (OHO) at Vanderbilt University Medical Center will also be contacted via emails and telephone calls.

Subjects will undergo an initial screen by the study coordinator or research staff to assess eligibility and ability to comply with the study requirements. Prior to each study visit, subjects on oral anti-diabetic medications will be asked to discontinue these medications 4 days prior to their study visit. Diabetic subjects will be instructed to monitor their pre-prandial blood glucose during this time and to contact the study physician if their blood glucose levels are greater than 250 mg/dL for two consecutive readings. The study physician may instruct the subject to initiate short-term insulin therapy or resume their oral anti-diabetic medications; in either case the subject will be excluded from the study. Subjects will be instructed to maintain their usual diet and physical activity levels for 1 week prior to each study visit and to arrive fasted for every visit (only water after dinner).

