## 11. Statistical Analyses

Sample Size: We hypothesize that Botox will reduce body weight, improve glucose tolerance, and augment lipid sensing during fasting and post-prandially, in Class I-III obese subjects. Our outcome measures for the effects of Botox are: body weight; area under the curve (AUC) for plasma levels of ghrelin, CCK, GIP, and GLP-1; and glucose AUC. Power calculation based on previous studies was performed using nQuery Advisor software. The number of subjects needed to detect a 15% decrease in body weight ( $n=16$ ), 10-15% decrease in plasma levels of gut peptides ( $n=14-16$ ), and a 10% decrease in glucose AUC ( $n=16$ ) was determined for an estimated 90% power (two-sided type I error rate = 0.05), with effect size of 0.25. We anticipate studying 20 subjects to account for attrition.

Statistical Analysis Plan: We will analyze pre- and post-intervention measurements at 1, 3, and 6 months using one-way repeated measures ANOVA for each outcome. Correlation between visits will be determined by the first-order autoregressive (AR1) rule which assumes that correlation among repeated measures decline exponentially with time. We will also determine the most optimal (1, 3, or 6 months) and inter time point differences for each outcome.

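### The hypothesis and aims are limited to type 2 diabetes, but the trial enrols and pools type 2 diabetes with pre-diabetes, so its result cannot be specific to type 2 diabetes

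*Combined protocol and SAP*

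**What the plan says.** The combined protocol and SAP describes the study population in three ways.

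- **Type 2 diabetes only.** The Section 2 hypothesis ends with the expectation that the injection will "improve duodenal nutrient sensing in obese, T2D subjects". Aim 1 is to "Determine if Botox injected into the duodenum reduces body weight in obese, type 2 diabetic subjects", Aim 2 to "Determine if Botox injected into the duodenum improves glucose tolerance in obese, type 2 diabetic subjects", and Aim 3 uses the same population for nutrient sensing. Pre-diabetes is not mentioned in Section 2.
- **Type 2 diabetes or pre-diabetes.** The study summary at the end of Section 3.2 says "We will recruit obese subjects with pre-diabetes or T2D for the proposed clinical study for 5 visits". Inclusion criterion 3 in Section 4 reads "Having established diagnosis of Type 2 diabetes or pre-diabetes". Section 5 recruits 20 subjects from both groups and gives no split.
- **Obesity only.** Section 11 restates the hypothesis "in Class I-III obese subjects" and does not mention glycaemic status.

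The planned analysis in Section 11 is a one-way repeated measures ANOVA of the baseline, 1-, 3- and 6-month values, with AR(1) correlation. There is no term, stratum, subgroup or separate summary by status. Section 12 does not discuss the mix.

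Section 5 also has a rule for diabetic subjects during the medication pause before each study visit. Those with two consecutive readings above 250 mg/dL contact the study physician, and those then told to start insulin or resume oral drugs leave the study.

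**The concern.** A trial could follow this protocol exactly, enrol few or even no subjects with type 2 diabetes, and still report its result against three aims written for type 2 diabetes. The reader of that report could not tell from the pooled mean which group it describes.

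The point bears most on Aim 2. If glucose AUC responds differently in the two groups, the pooled change depends on a mix that the plan neither sets nor reports. Body weight (Aim 1) is less exposed.

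The Section 5 rule adds to this. It can remove only diabetic subjects, and it recurs with the study visits, so the completers may hold a smaller share of type 2 diabetes than the enrolled group. Nothing in the plan would show that shift. The rule itself is a clinical matter and is not questioned here; the point is only its effect on who is analysed.

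**Working it through.** **Step 1. The population, section by section.**

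| Place | Population | Role of status |
|---|---|---|
| Section 2, hypothesis and Aims 1-3 | type 2 diabetes | defines the question |
| Section 3.2, study summary | pre-diabetes or type 2 diabetes | no split |
| Section 4, criterion 3 | type 2 diabetes or pre-diabetes | no minimum or cap |
| Section 5 | prediabetes or type 2 diabetes, 20 in all | no split; exit rule for diabetic subjects only |
| Section 11 | obesity classes I-III | none |

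The mismatch needs no calculation. Section 2 is narrower than every later section.

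**Step 2. What the planned model estimates.** With visit as the only factor, each mean change is a weighted average: share with type 2 diabetes × their mean change + share with pre-diabetes × their mean change. The plan fixes neither share. Each subject is compared with their own baseline, so a difference in starting level between the groups does not bias this average. Only a difference in response makes it depend on the mix.

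**Step 3. The plan's sample size.** Inputs from Section 11: 90% power, two-sided alpha 0.05, effect size 0.25, n = 16 for body weight and for glucose AUC, 20 enrolled. The definition of 0.25 and the value of the correlation are not given.

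Assume that 0.25 is a variance ratio, that is, variance of the visit means / [SD²(1 − ρ)], with four time points. Then λ = n × 4 × 0.25 = n, with 3 and 3(n − 1) degrees of freedom.

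- n = 15: λ = 15, df 3 and 42, power 88.8%.
- n = 16: λ = 16, df 3 and 45, power 91.0%.

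The smallest n with at least 90% power is 16, as stated, and 16 / (1 − 0.20) = 20. The stated number is thus consistent with a single pooled cohort.

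**Step 4. Illustration: power within type 2 diabetes alone.** The diabetic share is not given, so the subset sizes are assumptions. The second reading takes 0.25 as Cohen's f with an assumed equal correlation of 0.5, so λ = n × 4 × 0.25² / (1 − 0.5) = n/2.

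| Completers with type 2 diabetes | 0.25 as variance ratio | 0.25 as Cohen's f, ρ = 0.5 |
|---|---|---|
| 8 | 57% | 30% |
| 10 | 69% | 39% |
| 12 | 79% | 47% |
| 16 | 91% | 61% |

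Only the first reading returns the plan's 90% at n = 16. Neither column applies to Aim 3, because the nutrient sensing test is done at visits 1 and 3 only.

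**Step 5. Would a model term for status help?** A status main effect (1 df) adjusts the overall level between subjects. It does not show whether change differs by status. That needs a status-by-visit term, with (2 − 1) × (4 − 1) = 3 df. To see what 16 completers could show, take a single change score and an assumed 8 versus 8 split: the noncentrality is d × √(8 × 8 / 16) = 2d with 14 df, and 80% power needs d of about 1.5 SD of the change score. Any such comparison is exploratory at this size.

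**The case against.** The strongest reply is that the population actually studied is clear. The study summary, eligibility and enrolment sections all name both groups, and Section 2 is the outlier. On that view the aims simply carry outdated wording, and pooling people with raised glucose is a defensible choice in a small pilot. This largely stands. It is why the remedy is mainly one of wording and reporting, and why the severity is limited.

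Four stronger readings are tempting, and the documents do not support them.

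- *The trial will draw its conclusion for type 2 diabetes.* Section 2 invites that, but Sections 11 and 12 speak of obese subjects and commit to no such conclusion.
- *Most of the 20 will be pre-diabetic.* Eligibility allows it, but no expected split is given.
- *The result is biased because the groups start from different glucose levels.* The comparison is within subject, so a different starting level alone does not bias the mean change. The documents give no glucose AUC by status.
- *The trial is underpowered for its question.* The subset figures in Step 4 concern a test that the plan does not contain, and they rest on an effect size that the plan does not define.

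What remains is that aims naming one population cannot be answered by a pooled estimate from another, and that the plan gives the reader no means of seeing the difference.

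**Conclusion.** The point holds as a mismatch between the stated question and the population studied. The hypothesis and Aims 1-3 are limited to type 2 diabetes, eligibility is not, and the analysis pools everyone. A pooled estimate from this trial cannot support a conclusion specific to type 2 diabetes.

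The size is minor to moderate. The sample size and the within-subject test are unaffected. How far the pooled answer departs from the answer for type 2 diabetes depends on the share with diabetes and on any difference in response, and the documents give neither. The possible shift of completers toward pre-diabetes follows from the wording of the Section 5 rule; how often the rule would be triggered is unknown.

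**What to change.** 1. Make the population the same in Sections 2, 4, 5 and 11 by restating the hypothesis and Aims 1-3 for obese subjects with type 2 diabetes or pre-diabetes.
2. Report the numbers enrolled, removed (with the reason, including the Section 5 glucose rule) and completed, by status.
3. Report change from baseline by status descriptively at each visit where the outcome is measured, glucose AUC above all.
4. State in Section 11 that no claim specific to type 2 diabetes will be made from the pooled analysis.
5. Do not add a status main effect for this purpose. If a model term is wanted, use status by visit (3 df) and label it exploratory.

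Status is known at entry, because criterion 3 requires an established diagnosis, so no new data, visits or subjects are needed. The cost is some rewording and one or two added tables. The downside is that the permitted claim becomes broader but less specific.
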